7.3.2 Participants randomised to DMARD arm

In this trial, DMARDs will be prescribed by the site, which will also take responsibility for arranging and checking the results of DMARD monitoring blood tests, and for issuing DMARD (DMARD may be posted to the participant from site pharmacy). The allowed DMARDs will be MTX or LEF.

In addition to usual care steroid therapy, participants in the DMARD arm will initially receive weekly oral methotrexate (MTX), co-prescribed with folic acid.

MTX will be started at 15mg weekly; this can be reduced to 10mg weekly if the higher dose is not tolerated.

If 10mg weekly MTX is not tolerated, or if MTX is ineffective, MTX may be switched to leflunomide (LEF) starting at 10mg daily. The starting dose will be increased to 20mg daily if tolerated, or reduced to 10mg every 2 days if not tolerated. The minimum LEF dose will be 10mg twice weekly. If this minimal LEF dose is not tolerated, DMARD will be stopped.

MTX will be co-prescribed with folic acid according to local practice; the folic acid dose will be at least 5mg weekly, and may be prescribed up to six days per week (folic acid is not generally given on the same day as MTX).

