13.1.19 Most frequently anticipated toxicities of MTX

In a systematic literature review (47), the pooled prevalence of adverse effects was 80.1% in RCTs of MTX, and 23% in observational studies. In RCTs 6.7% discontinued MTX due to adverse effects, whereas in observational studies 15.5% discontinued due to adverse effects.

Commonly reported side-effects of methotrexate include nausea (19.2% in RCTs), altered taste, abdominal pain or discomfort (9.3% in RCTs), diarrhoea (8.0% in RCTs), headache (8.5% in RCTs), dizziness (7.2% in RCTs), fatigue, and thinning of the hair (6.9% in RCTs) and mouth ulcer or soreness (7.8% in RCTs). These are often easily noticed by the participant because of the weekly administration. In this trial, these well-known adverse effects of MTX are not necessarily considered “toxicities” unless they are troublesome to the participant. Folic acid, 5mg up to six days per week, may help to alleviate many of these common side-effects. Management advice may also include review of diet, smoking cessation, mouthwashes for sore mouth or simple analgesia for headache, at the clinician’s discretion. An extra cup of strong coffee, or dark chocolate, the morning after MTX administration is sometimes recommended on the basis that caffeine antagonises adenosine signalling in the central nervous system and might alleviate the central nervous system side-effects of MTX (48).

MTX may cause mild cytopenia including neutropenia. Neutrophil counts below $1 \times 10^9/L$, if persistent on rechecking, would be an indication to stop MTX. Pancytopenia is rare and usually only seen in MTX overdose.

MTX-related pneumonitis is an idiosyncratic reaction and is very rare (47): it was reported in <0.1% of participants in RCTs.

Abnormalities of liver function tests including AST/ALT are frequently observed in patients receiving MTX; in the meta-analysis (47) the pooled prevalence of any elevated liver enzyme was 15.3% in 6 RCTs. The concern is that MTX may have a profibrotic effect; it is contra-indicated in participants who already have liver cirrhosis. A study of liver stiffness using Fibroscan (49) in participants receiving MTX showed no correlation with cumulative MTX exposure but significant correlations with markers of obesity (body mass index, waist circumference).

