13.3 LEFLUNOMIDE REGIMEN

13.3.1 MTX wash-out

MTX must be stopped before LEF is commenced (they should not be taken together in this trial).

MTX polyglutamates may be retained in tissues for some weeks after MTX cessation, and therefore a wash-out period of at least 2 weeks is recommended before starting LEF; this may be extended to 8 weeks where required.

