13.3.10 Duration of Treatment

Participants in the DMARD arm will commence LEF only after stopping MTX. Providing it is tolerated and there is no toxicity, the LEF treatment will continue until the final study visit at 18 months.

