As for the primary outcome, if any steroid medications other than prednisolone are prescribed, these will be converted to an agreed “prednisolone equivalent dose” prior to analysis.

Safety

Adverse events (AEs) of Special Interest reported over 18 months post randomisation will include those relevant to PMR and/or investigational medicinal product.

Serious adverse events (SAEs) and SUSARs regardless of relationship to PMR or investigational product reported over 18 months post randomisation.

Glucocorticoid toxicity

Glucocorticoid toxicity is defined as per the OMERACT Glucocorticoid Core Domain Set (infection, diabetes, hypertension, fracture) adapting measures from the Glucocorticoid Toxicity Index (67)

Time to development of GCA

Time to development of GCA (defined as rheumatologist-confirmed and treated according to GCA treatment protocols specified in 2020 BSR guideline, without the diagnosis later being revised from GCA during the 18 month period) will be defined as the duration between randomisation and date of GCA diagnosis. Participants who are not diagnosed with GCA during follow-up will be censored at 18 month, or else at date of death or withdrawal.

Proportion of participants diagnosed with adrenal insufficiency

The proportion of participants who are identified as diagnosed with adrenal insufficiency will be the proportion of participants who either have a low value of 9am cortisol test, or an intermediate value followed by a positive short synacthen test, at any point during follow-up. Adrenal insufficiency screening tests (9am cortisol) will be conducted within the trial but confirmation of physician diagnosis of adrenal insufficiency, will be recorded, along with the relevant date and actions taken in response.

Deaths

Deaths from all causes over 18 months post randomisation. Date of death will be recorded, and time to death will be derived as days from randomisation to death.

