18.3 ANALYSIS OF SECONDARY OUTCOME MEASURES

PMR symptom severity measures, PMR activity score, and Patient-reported quality of life measures over 18 months: analysis of PMR-IS domain scores, health-related quality of life (EQ-5D-5L Utility), PMR-Activity Score will use multivariable repeated measures linear regression adjusting for minimisation factors, baseline value, treatment group, baseline-by-time interaction (if appropriate), age, time, and time-by-treatment group interaction. Centre will be fitted as a random effect, if feasible and has a positive variance component. Time will be fitted as a continuous variable, and the estimated time-by-treatment interaction effect with 95% CI and significance will be presented.

Time to steroid cessation, Time to PMR relapse: time to event will be calculated and summarised using Kaplan-Meier estimates. Adjusted hazard ratios will be estimated using Cox proportional hazards regression or parametric alternative, with covariates for minimisation factors (fitting centre as a random effect, if feasible) age and treatment group, and reported with 95% CI.

Steroid free remission at week 80 post randomisation will be summarised by treatment group and overall.

Number of relapses over time: A multivariable negative binomial regression model will be used to explore the number of relapses reported over follow-up time with an offset term for time at risk, adjusting for minimisation factors, age and treatment group. Centre random effects will be explored, assuming a Gamma distribution. Adjusted difference in rate of relapse with 95% CI will be reported.

Cumulative prednisolone-equivalent dose prescribed: A multivariable linear regression model will be fitted to log (cumulative glucocorticoid dose), adjusting for minimisation factors (fitting centre as a random effect, if feasible) age and treatment group. Adjusted mean fold difference in cumulative glucocorticoid dose with 95% CI will be reported.

Safety: The number of adverse events of special interest related to PMR or trial treatment, serious adverse events and SUSARs, in number of unique patients, will be reported by treatment received (MTX/LEF/Both/Neither) and by severity.

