Time to development of GCA will be summarised using Kaplan-Meier estimates. Adjusted hazard ratios will be estimated using Cox proportional hazards regression or parametric alternative, with covariates for minimisation factors (fitting centre as a random effect, if feasible) age and treatment group, and reported with 95% CI.

Adrenal insufficiency: The proportion of participants considered to be experiencing adrenal insufficiency will be reported in both groups.

Deaths: Number of deaths from all causes over 18 months post randomisation and time to death will be summarised by treatment received

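### The safety columns MTX/LEF/Both/Neither do not fit a design in which LEF only follows MTX: MTX events in switchers fall under Both, and no tabulation of these events by randomised arm is stated

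*Protocol*

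**What the plan says.** Section 18.3 (Safety) fixes the display of adverse events of special interest, SAEs and SUSARs: counted in unique patients, they "will be reported by treatment received (MTX/LEF/Both/Neither) and by severity". For deaths, the same section says that the number and "time to death will be summarised by treatment received". Section 16.2.2 sets the clock: "time to death will be derived as days from randomisation to death".

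The treatment sections fix the order of the two drugs:
- Section 7.3.2: "participants in the DMARD arm will initially receive weekly oral methotrexate (MTX), co-prescribed with folic acid". A contraindication to methotrexate is an exclusion (section 8.2), so there is no planned direct route to leflunomide.
- Section 13.3.10: "Participants in the DMARD arm will commence LEF only after stopping MTX".
- Section 13.3.1: the two drugs are not to be taken together, and "a wash-out period of at least 2 weeks is recommended before starting LEF", which may be extended to 8 weeks.
- Sections 7.3.2 and 13.1.14: methotrexate may be given up for intolerance or for inefficacy.

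On how often methotrexate is stopped, section 13.1.19 cites a systematic review: "In RCTs 6.7% discontinued MTX due to adverse effects, whereas in observational studies 15.5% discontinued due to adverse effects".

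**The concern.** The four classes would suit a trial in which a participant could take either drug, both at once, or none. Here the drugs come in a fixed order, and the reason for moving from the first to the second is often an adverse effect of the first. Class membership therefore depends on the outcome being tabulated.

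Three things are at stake. First, methotrexate events in participants who leave the drug because of them move out of the MTX column and are pooled with whatever happens later on leflunomide. Second, Neither combines the usual-care arm with DMARD-arm participants who never took a dose, so no column is a randomised group. Third, the counts carry no time at risk, although time on each drug will vary: methotrexate may be stopped early, interruptions of up to 8 weeks are allowed (section 13.4.1), and the DMARD may be stopped once six months have passed since the last steroid. Section 18.3 uses a time-at-risk offset for relapses but not for adverse events.

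The protocol states these columns, so an analysis plan that follows it would carry the problem into the final report.

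**Working it through.** **What the labels can mean.** The protocol says treatment received and does not define it. There are two candidate readings.

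| Reading | LEF | Both |
|---|---|---|
| Drugs received by the end of follow-up | no planned members | MTX, then LEF |
| Drug being taken when the event began | LEF phase | empty, since the drugs are not taken together |

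Counting unique patients and having a Both class point to the first reading. On the second, Both serves no purpose. One label fails to fit the design on either reading.

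**No stated figure is in dispute.** The only figure needed from the sample-size section is the arm size: 200 participants at 1:1 gives 200/2 = 100 in the DMARD arm, all taken here as starting methotrexate.

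**Illustration of the MTX column (first reading).** Let E be the number per 100 starters with a given event on methotrexate, k the number who stop for adverse effects and switch, and q the share of those k who had the event. Then

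MTX column = (E − qk) / (100 − k).

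Inputs from section 13.1.19 are E = 19.2 (nausea in RCTs) and k = 6.7 or 15.5. Assumptions are that every such stopper switches and that q is 0.5 or 1.

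| k | q | Calculation | MTX column | True risk |
|---|---|---|---|---|
| 6.7 | 0.5 | (19.2 − 3.35)/93.3 | 17.0% | 19.2% |
| 6.7 | 1 | (19.2 − 6.7)/93.3 | 13.4% | 19.2% |
| 15.5 | 0.5 | (19.2 − 7.75)/84.5 | 13.6% | 19.2% |
| 15.5 | 1 | (19.2 − 15.5)/84.5 | 4.4% | 19.2% |

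In these scenarios 50% to 100% of the Both column already has the event before any leflunomide is taken. With an assumed 10% leflunomide risk in those still free of the event, the lower end is 0.5 + 0.10 × 0.5 = 55%.

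**Sensitivity to the event rate.** The same section gives any-adverse-effect prevalences of 80.1% (RCTs) and 23% (observational studies). Paired with the matching stopping rates and q = 1:
- RCTs: (80.1 − 6.7)/93.3 = 78.7%, a shift of 1.4 points.
- Observational: (23 − 15.5)/84.5 = 8.9%, a shift of 14.1 points.

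**Direction.** The MTX column understates the risk only if the event is commoner among all switchers than among all starters. Switchers for inefficacy who had no event pull the other way. With E = 19.2, k = 6.7 and q = 1, the bias cancels when such switchers number 6.7/0.192 − 6.7 = 28.2 per 100. With q = 0.5 it cancels at 3.35/0.192 − 6.7 = 10.7 per 100.

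**What can still be recovered.** If column sizes are printed, the methotrexate risk lies between (MTX events)/100 and (MTX + Both events)/100. For k = 15.5 and q = 1 that is 3.7% to (3.7 + 15.5)/100 = 19.2%. The leflunomide risk cannot be isolated, because events in Both carry no drug label.

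**The case against.** **The SAP will settle it.** Section 18.1 says that analyses and populations will be predefined there, and denominators and attribution rules usually are. This stands for the detail. It does not stand for the columns, which the protocol has already chosen.

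**The trial tests a strategy.** Section 15.2 says so, and any DMARD against Neither can be had by collapsing columns. That is correct, but the collapsed contrast is still by treatment received and not by arm. Giant cell arteritis and adrenal insufficiency, also safety outcomes, are handled by group in section 18.3; these events and deaths are not.

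**Stronger readings that the documents do not support.**
- A reader might infer that the LEF column must be empty. Section 16.1 foresees crossover, so off-plan use could put a few participants there.
- A reader might infer that neither drug's harm can be read at all. The methotrexate risk can be bounded as shown, and SAEs carry dates and a causality assessment (section 15.4.1), although the stated table does not use them.
- A reader might infer that Both is all methotrexate toxicity, or that the MTX column must understate. Inefficacy switchers also enter Both, the listed events count only from CTCAE grade 2 (sections 15.2.2 and 15.2.3), and intolerant participants who never start leflunomide stay under MTX.
- A reader might infer that the DMEC would be misled. Section 19.3 lets it see data by randomised group or by treatment received.
- A reader might infer an immortal-time bias in a survival comparison. Switchers must indeed live to the switch while the clock starts at randomisation, but time to death is only summarised: section 18.3 plans no Kaplan-Meier curve or hazard ratio for it, and does not repeat the four classes there. This is a minor point.

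**Conclusion.** The point holds as a mismatch between the stated safety columns and the sequential design. As specified, the table yields no methotrexate risk among all methotrexate starters, no separate leflunomide risk and no comparison by randomised arm. It rests on reading treatment received as drugs received over follow-up. That is an inference, but it is the only reading under which Both has members.

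The size cannot be fixed from the documents. It depends on three unknowns:
- the share who switch for intolerance: 6.7% to 15.5% only if every such stopper switches, from a review in rheumatoid arthritis. Section 13.1.14 presents the switch as expected unless contraindicated, sections 7.3.2 and 13.2 as optional, and these passages need reconciling;
- the number who switch for inefficacy;
- the reportable event rate, for which the 19.2% nausea figure is a stand-in and not a grade 2 rate.

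The 4.4% to 17.0% range shows that the distortion can be material. It is not a forecast. The plan should be changed, mainly to protect the final report.

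**What to change.** 1. Report adverse events of special interest, SAEs, SUSARs and deaths by allocated arm.
2. Within the DMARD arm, replace the four classes with attribution by drug at onset: from the first methotrexate dose until leflunomide starts, and from the first leflunomide dose onwards. State in advance how events in the wash-out gap are assigned.
3. Give the number of starters of each drug and the person-time at risk as denominators.
4. Show DMARD-arm participants who never started within their own arm, not with usual care.
5. Summarise time to death from randomisation by allocated arm.

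The cost is wording in section 18.3 and slightly more programming; no clinical rule changes. DMARD use and adverse events are already reviewed at the follow-up contacts (section 14.2), and time of switching is already to be described (section 18.4). Two limits remain. Leflunomide denominators will be small. Onset near a switch may be uncertain for non-serious events, because the protocol states start dates only for SAEs and contacts are up to 12 weeks apart.

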18.4 PRE-SPECIFIED EXPLORATORY ANALYSES

To classify symptom trajectories in relapsing PMR using methods exploring correlation structures and ‘groupings’ of symptoms, summary statistics of baseline characteristics and / or responses to participant-completed questionnaires and other clinic outcomes will be presented. More detailed analyses will be detailed in the analysis plan.

To describe characteristics of participants switching from MTX to LEF and time and reasons for switching, summary statistics of baseline characteristics will be explored between groups who switch and do not switch.

To describe effectiveness of MTX vs LEF (within the DMARD arm) certain outcome measures will be reanalysed, only including participants randomised to the DMARD arm. The treatment group parameter will be replaced with an indicator variable corresponding to the chosen DMARD. If feasible, analysis models will first include terms that are necessary for any multi-level modelling, then where possible terms for the minimisation factors and age.

To explore potential baseline predictors of adverse outcomes, attention will be restricted to only those events reported most frequently. Since the full study sample size may have limited scope to develop robust multivariable prediction models, models will be limited in the numbers of variables included, to reduce the risk of overfitting. Appropriate parameters to permit sample size calculation of cohort sizes needed to develop such a model will be reported. (72).

To describe inflammatory markers and steroid dose at time of relapse, summary statistics of inflammatory markers and steroid dose at the timepoint closest to relapse will be reported.

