3. TRIAL SUMMARY

Trial Title	Steroid-Reducing Options for ReLapsING PMR (STERLING-PMR): a pragmatic, randomised trial to compare the clinical and cost-effectiveness of adding immunomodulation to steroid-tapering treatment for patients with relapsing PMR, versus steroid-tapering alone.
Short title	STERLING-PMR
Clinical Phase	Phase III
Study Sites	The Queen Elizabeth Hospital / University of Adelaide The Austin Hospital The University of Western Australia / Fiona Stanley Hospital
Trial Design	Multi-centre, Phase III, parallel-group, open-label, randomised controlled trial with internal pilot. The screening period of up to 6 weeks, a 80 week open label study period. At baseline, each subject will switch from oral glucocorticoids obtained from independent sources to oral prednisolone provided by the t the equivalent dose that the subject was taking just prior to the Baseline Visit, rounded up to the nearest 1 mg The study will consist of 4 study visits at site over 18 months. In addition, site research teams will conduct telephone assessments with participants from both arms at weeks 4, 8, 12, 36, 48, 60 and 72. Participants will be randomised in a 1:1 allocation ratio to receive either usual care alone or usual care plus DMARD.
Trial Participants	Patients with polymyalgia rheumatica (PMR) who are (1) receiving steroid treatment and (2) who have previously experienced at least one relapse of PMR.
Planned Sample Size	50 (of the 200 total)
Planned Number of Recruiting Sites	3
Follow-up schedule	7 study visits at site over 18 months (screening, baseline,12,24,36,48 and 80 weeks) In addition, site research teams will conduct telephone assessments with participants from both arms at weeks 4, 8, , 60 and 72. CTRU will manage the administration of monthly questionnaires sent to participant either by post or electronically.

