6.4 EXPLORATORY OBJECTIVES

Exploratory objectives are to:

- classify symptom trajectories in relapsing PMR
- describe the characteristics of participants who switch from MTX to LEF
- explore comparative effectiveness of MTX versus LEF
- explore predictors of adverse outcomes in PMR
- describe inflammatory markers and steroid dose at time of relapse

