7.3 TREATMENT REGIMENS

7.3.1 Steroid management (both arms)

Participants in each arm of the trial will continue to receive usual care for their relapsing PMR, including a long-term tapering course of steroid therapy, alongside any concomitant medications that may be clinically indicated to prevent or manage steroid side-effects.

If the PMR symptoms remain well-controlled during the steroid taper without any further relapses, and the participant is able to stop taking steroid entirely, they will be able to do so just as they do in usual care.

If there is a relapse of PMR disease activity, the steroid may be re-started, or the dose may be held constant for longer than originally planned, or the dose may be escalated; as in usual care this will be individualised to the participant according to the clinical discretion of the PI.

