DMARD Use Review if applicable			x	x	x	x	x	x		
Medical History		x	x	x	x	x	x			
AEs/SAEs review			x	x	x	x	x	x		
Chest X-Ray*	x									
Pregnancy Test	x									
RF [§]	x									
ACPA [§]	x									
U&E	x	x	x	x	x	x	x		x	
FBC	x	x	x	x	x	x	x		x	
Liver Function Test	x	x	x	x	x	x	x		x	
HbA1C		x	x	x	x	x	x			
CRP (Also needed for PMR-AS)	x	x	x	x	x	x	x			
ESR		x	x	x	x	x	x			
Physical Examination	x	x	x	x	x	x	x			
Vital Signs	x	x	x	x	x	x	x			
PMR Activity Score		x	x	x	x	x	x			
(PMR-AS) Number of minutes of morning stiffness		x		x				x		
(PMR-AS) Upper limb elevation / active shoulder abduction		x		x				x		
(PMR-AS) VAS global assessment (physician)		x		x				x		

Steroid Free Remission								x		
------------------------	--	--	--	--	--	--	--	---	--	--

* a report from a chest x-ray performed within the 6 months prior to the screening visit is acceptable to confirm eligibility providing that no evidence of interstitial lung disease or tuberculosis or active.

† As a guide the British Society for Rheumatology DMARD monitoring guidelines recommend FBC, U+E and LFT: every two weeks until on stable dose for six weeks, then monthly for three months and quarterly thereafter. Blood pressure should be measured at the same timepoints as these blood tests.

‡ Providing the results of the prior test are acceptable (see section 13.4.1), a window will be allowed one week either side of the scheduled date during the first six weeks, two weeks either side of the next scheduled date for the next three months and one month either side of the next scheduled date thereafter

§ Rheumatoid factor (RF) and anti-citrullinated peptide antibody (ACPA/anti-CCP) both within local laboratory reference range at or within the 12 months prior to the screening visit

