14.7 WEEK 12, 24,36, 48 and WEEK 80 FOLLOW-UP STUDY VISITS

These visits will be conducted in clinic, face to face at 24 and 80 weeks post randomisation. The following data will be collected.

- Steroid and DMARD use
- (S)AE reporting (including Adverse Events related to glucocorticoid toxicity e.g. infection, diabetes, hypertension and fracture)
- Relevant medical history
- Urea & Electrolytes (U&E) test
- Full blood count
- Liver function test
- PMR Activity Score (52), requiring: (week 24 & 80 only)
 - CRP;
 - Physician VAS assessing disease activity;
 - Number of minutes of morning stiffness;
 - Upper limb elevation / active shoulder abduction; (EUL) graded as 0-3
 - Participant pain VAS (0-10) (see section 14.10)
- Weight
- Hip and waist circumference (week 80 only)
- HbA1C test(week 24 & 80 only)

- ESR test
- Physical examination – MSK system including elevation of upper limbs, joint swelling/tenderness/limitation of movement, and vascular including temporal arteries
- Vital Signs – including, BP, heart rate, temperature
- Participant questionnaires (see section 14.10)

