14.10 PARTICIPANT QUESTIONNAIRES

Participant-reported steroid dose, and whether this needed to be increased due to increase in PMR symptoms, will be collected via the Steroid Use Questionnaire. This questionnaire will be administered every four weeks from week 4 to week 80. Cumulative (prednisolone-equivalent) steroid dose will be estimated from data provided in the Steroid Use Questionnaire, interpolating if necessary. PMR relapse date(s) and date(s) of steroid cessation, if applicable, will be calculated from the data provided in the Steroid Use Questionnaire, allowing time to relapse, number of PMR relapses and time to steroid cessation and time to steroid-free remission to be calculated during the analysis of the trial.

PMR symptom severity will be captured via the PMR-IS administered at baseline (week 0) and weeks 12, 24, 36, 48, 60, 72 and 80 post randomisation.

Participant health related quality of life will be captured via the EQ-5D-5L questionnaire. This will be administered at baseline (week 0) and weeks 12, 24, 36, 48, 60, 72 and 80 post randomisation.

Participant healthcare resource use will be collected at baseline (week 0), and weeks 12, 24, 36, 48, 60, 72 and 80 post randomisation.

In addition, questionnaire booklets at baseline (week 0) and weeks 24 and 80 post baseline will include a Visual Analogue Scale (range 0 to 100mm) on which participants will mark the level of Pain they experience.

This will be used to score the PMR Activity Score. Booklets including this VAS will be distributed separately, as professional printing is required to ensure VAS lengths are exactly 100mm.

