16.2.2 Clinical outcomes

Time to steroid cessation

Time to steroid cessation, will be defined as the duration between date of randomisation and date at which participants report a current prednisolone dose of zero and there is sustained discontinuation of all steroids.

Sustained discontinuation of steroids will be defined as not taking any further steroids for the duration of follow-up.

Participants that have continued to take steroids/prednisolone to the end of follow-up or who had a temporary cessation of steroids will be censored at 18 months. Those who die, withdraw and/or are lost to follow-up will be censored at the point of death/withdrawal or loss to follow-up.

Time to steroid-free remission

Where participants report a current-oral steroid dose of zero a decision as to whether or not steroid-free remission is achieved will be agreed between the participant and physician at the week 80 assessment.

Time to PMR relapse

PMR relapse, which will be participant reported, will be defined as an increase in PMR symptoms sufficiently severe to require alteration of the steroid dosing plan. Participants will be asked every month whether they have had to adjust their planned steroid dosing plan due to an increase in PMR symptoms (participant reported relapse).

Time to PMR relapse will be defined as the duration between randomisation and date of PMR relapse. Participants that have not relapsed during follow-up will be censored at 18 months, or at date of death or withdrawal.

Note: There is no universally agreed definition of relapse in PMR, therefore, a pragmatic approach will be taken.

Number of PMR relapses

PMR relapse will be defined as an increase in PMR symptoms sufficiently severe to require alteration of the steroid dosing plan. The count of the number of PMR relapses will be derived as the sum of all relapses over the time at risk.

Time at risk will be defined as the duration between date of randomisation and the earliest of date of end of follow-up, death or withdrawal.

Cumulative (prednisolone-equivalent) steroid dose prescribed

Cumulative (prednisolone-equivalent) steroid dose prescribed over 18 months post randomisation.

The total amount of oral steroid prescribed during the trial will be assessed from GP records of all prednisolone prescriptions issued during the trial, and will be collected at 18 months post randomisation.

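### The nearest-timepoint rule for CRP/ESR at relapse (18.4) sets no direction or maximum distance, so it pools draws from before and after the steroid change, often weeks from the relapse

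*Protocol*

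**What the plan says.** Protocol 6.4 sets the exploratory objective to "describe inflammatory markers and steroid dose at time of relapse". Section 18.4 delivers it in one sentence: "summary statistics of inflammatory markers and steroid dose at the timepoint closest to relapse will be reported". It gives no direction in time and no maximum interval.

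Section 16.2.2 defines relapse as "an increase in PMR symptoms sufficiently severe to require alteration of the steroid dosing plan". It is participant-reported, and 14.10 states that "PMR relapse date(s) and date(s) of steroid cessation, if applicable, will be calculated from the data provided in the Steroid Use Questionnaire". The relapse date therefore comes from a questionnaire, not from a visit with a blood draw.

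The Schedule of Events (14.2) has a row "CRP (Also needed for PMR-AS") ticked at screening, baseline and weeks 12, 24, 36, 48 and 80. The ESR row is ticked at baseline and the same follow-up weeks. These are the site visits in the Trial Summary: "7 study visits at site over 18 months (screening, baseline,12,24,36,48 and 80 weeks"). The telephone contacts (14.6) collect neither marker, and the suggested DMARD monitoring (14.9) is blood count, renal and liver tests.

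Section 14.7 differs on CRP. It lists CRP only as a component of the activity score: "PMR Activity Score (52), requiring: (week 24 & 80 only"). ESR appears there without a week limit.

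Steroid dose is recorded much more finely. The 4-weekly questionnaire asks for the current dose and the dose in each of the preceding four weeks (7.4.2).

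**The concern.** CRP and ESR are the protocol's own laboratory markers of PMR inflammation (5.1), and 5.2 describes re-escalation of steroid as bringing symptoms back under control. A value drawn after the plan was altered may reflect the response to the alteration. A value drawn many weeks before may reflect a quiet period. On the protocol's own account, both would tend to be lower than the value at the relapse.

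The rule in 18.4 mixes the two kinds and offers the result as the answer to an objective about the time of relapse. A reader could conclude that relapses occur with lower inflammatory markers than they do. Nobody could tell from the summary how much of it came from before the change, from after it, or from far away.

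**Working it through.** The protocol gives no figure to reproduce and no distribution of relapse times. The check places relapses on the scheduled draw weeks.

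**Inputs**
- Draw weeks from 14.2: 0, 12, 24, 36, 48, 80. The gaps are 12, 12, 12, 12 and 32 weeks, in total 80. The screening CRP is never nearer than baseline for a relapse after randomisation.
- Relapse times: assumed uniform over weeks 0–80 and independent of visits.

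**Formulas.** For a relapse uniform in a gap of length L, the nearest draw is the later one with probability 1/2, the mean distance to the nearest draw is L/4, and the maximum is L/2. Weighting each gap by L/80 gives a mean distance of ΣL²/(4 × 80).

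**Results for the 14.2 schedule**
- Nearest draw after the relapse: 50%.
- Mean distance: (4 × 144 + 1,024)/320 = 1,600/320 = 5.0 weeks.
- Maximum distance: 32/2 = 16 weeks.
- Nearest draw within 2 weeks either side: 5 gaps × 4 weeks = 20; 20/80 = 25%.
- A draw in the 2 weeks before the relapse: 5 × 2 = 10; 10/80 = 12.5%.
- Nearest draw more than 4 weeks away: 4 × (12 − 8) + (32 − 8) = 40; 40/80 = 50%.

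**How far the 50% moves**

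| Assumption | Share drawn after the change |
|---|---|
| Uniform, baseline may be matched | 50% |
| Uniform, baseline may not be matched: (12 + 3 × 6 + 16)/80 | 57.5% |
| Constant hazard, 50% relapsing by week 80 (without baseline) | 48% (58%) |
| Constant hazard, 80% relapsing by week 80 (without baseline) | 46% (60%) |
| 10% of relapses declared at a scheduled visit, blood drawn before the change: 0.9 × 50% | 45% |
| 30% so declared: 0.7 × 50% | 35% |

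The ±2-week visit window moves these shares by about one percentage point or less. A reasonable range is 35–60%. The most extreme case tried on this schedule, with all relapses in weeks 0–48 and baseline not matched, gives (12 + 3 × 6)/48 = 62.5%.

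**Would a stricter rule alone repair it?** Using only the last draw on or before the relapse gives a mean lag of ΣL²/(2 × 80) = 1,600/160 = 10 weeks and a maximum of 32. Requiring that draw to lie within 2 weeks keeps 12.5% of relapses and drops 87.5%. Rewording the analysis makes the summary interpretable, but it does not create values at relapse.

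**CRP if 14.7 is followed** (weeks 0, 24, 80): mean distance (576 + 3,136)/320 = 11.6 weeks, maximum 28, and 8/80 = 10% within 2 weeks. This follows from the conflict between 14.2 and 14.7 and concerns CRP only.

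**The case against.** **Data windows belong in the SAP.** Section 18.1 says that analyses will be predefined there, and nothing in 18.4 forbids a before/after split. This stands in part: a SAP could refine the rule. But 18.4 states a rule and does not leave it open, and that rule is the fault. Nor can a SAP supply marker values that were never scheduled or recorded.

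**The approximation is disclosed**, because 18.4 says that the values come from the nearest timepoint. That is true, but the disclosure does not show direction or distance, which are what a reader needs.

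**A stronger reading is tempting on four counts, and the documents do not support it.**
- A reader might take one half as a property of the trial. It rests on an assumed spread of relapses. The site manages the taper (7.2), so some relapses may come to light at a scheduled visit with blood drawn first.
- A reader might infer that every later draw follows a dose increase. Section 7.3.1 says that on relapse "the steroid may be re-started, or the dose may be held constant for longer than originally planned, or the dose may be escalated", so an altered plan can be a dose held for longer.
- A reader might infer that steroid dose at relapse is as badly placed as the markers. It is not: doses are recorded for each week and relapse dates come from the same questionnaire, so the ambiguity is about one week.
- A reader might use the 11.6-week distance as evidence against the nearest-timepoint rule. It arises from the separate conflict over CRP weeks.

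**The analysis is minor.** This stands: it is one of five exploratory objectives, with summary statistics only.

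**Conclusion.** The concern holds for CRP and ESR. Under 18.4 as written, values from before and after the steroid change are pooled without limit on distance. With relapses spread evenly and independent of visits, about half of the nearest draws follow the change (roughly 35–60% under the other assumptions tried). The mean distance is 5 weeks, the maximum 16, and 25% lie within 2 weeks. Distance is as much a problem as direction.

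The likely effect is to understate CRP/ESR at relapse. That direction rests on the protocol's account of the markers and of steroid response; the size of the bias cannot be estimated from the document. For steroid dose, only a small clarification is needed. The primary, secondary and safety results and the sample size are untouched.

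**What to change.** 1. In 18.4, replace the single nearest-timepoint summary for CRP/ESR with two: draws on or before the steroid change, and draws after it. Report the interval to relapse for each and the number of relapses with no draw within a stated window. A strict pre-change window, such as 14 days, can be a sensitivity summary. It should not be the sole rule, because on the schedule in 14.2 it would keep only about 12.5% of relapses.
2. Define steroid dose at relapse as the last weekly questionnaire dose before the reported change.
3. Let the eCRF record any CRP or ESR already taken in routine care at the relapse, with its date. No new test is involved. Do this while data are being collected, since such results are hard to recover later.
4. Separately, reconcile 14.2 and 14.7 on the weeks at which CRP is drawn. Section 7.4.1, which schedules in-person follow-up at weeks 24 and 80 only, must be brought into line with whatever is settled.

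The cost is a few lines of analysis wording and one optional eCRF field. The downside is smaller subgroups in the summary.
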